8 SAFETY MONITORING AND REPORTING

8.1 Adverse Events

An AE is any untoward medical occurrence associated with the use of an investigational product in humans, whether or not considered related to the investigational product. This includes any occurrence that was new in onset or aggravated in severity or frequency from the baseline condition.

In this study, symptoms of CRS are collected as part of the primary and secondary endpoints. Changes or worsening of symptoms of CRS should not be reported as AEs. All events that meet the definition of a SAE will be reported as SAEs, regardless of whether they are protocol-specific assessments.

Abnormal results of diagnostic procedures, including laboratory test abnormalities, or from the nasal examination are considered AEs if they result in:

- discontinuation from the study treatment or discontinuation from the study
- require treatment or any other therapeutic intervention
- require further diagnostic evaluation which confirms a clinically significant abnormality (excluding a repetition of the same procedure that rules out an abnormality)
- are associated with clinical signs or symptoms that would have a significant clinical impact, as determined by the investigator

Subjects are encouraged to report AEs spontaneously or in response to general, non-directed questioning. All non-serious AEs are to be followed until the subject completes the study or is lost to follow-up.

Timely, accurate, and complete reporting and analysis of safety information from clinical studies is crucial for the protection of subjects, is the responsibility of the investigators and the Sponsor, and is mandated by regulatory agencies worldwide.

Each AE is to be documented on the CRF with reference to intensity, date of occurrence, duration, frequency, treatment, action taken regarding study drug, and outcome. Furthermore, each AE is to be classified as being serious or non-serious. Additionally, the investigator has to assess whether the AE is drug related (adverse drug reaction) or not. Changes of AEs and dates of ending have to be documented on the CRF.

Surgical procedures, planned before enrollment of the subject in the study, are not considered AEs if the condition(s) was (were) known before study inclusion. In the latter case, the medical condition should be reported in the subject's medical history.

For the purposes of this study, the period of observation for collection of AEs extends from the time the subject gives informed consent until completion of the end-of-study visit or an early termination visit. SAEs will be reported through 30 days after the last dose of study drug administration.

The maximum severity (intensity) of the AE will be categorized by the investigator as shown in [Table 5](#).

Table 5: Adverse Event Severity

Code	Descriptor	Definition
1	Mild	The subject is aware of the symptom, but easily tolerates it
2	Moderate	The subject has discomfort enough to cause interference with usual activity.
3	Severe	The subject is incapacitated to work or perform the usual activities

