Subjects in the open-label studies also had considerable improvement in symptoms and in objectively observed local signs of disease. A substantial proportion of subjects with intranasal edema at study entry no longer had evidence of edema on examination at study completion, a finding consistent with an intranasal deposition profile that places topically -acting fluticasone propionate in the areas beyond the nasal valve including the area of the middle meatus/OMC. In subjects with polyps, extensive reductions in polyp grade were observed and polyps were eliminated from at least 1 side of the nose in approximately 50% of subjects. In the 12-month study the improvement in polyp grade, polyp elimination, and edema increased over time, suggesting benefit with continued treatment over the observed period.

The most commonly reported adverse events (AEs) in the active treatment groups were associated with local effects at the site of administration in the nasal cavity (epistaxis, nasal congestion, nasal mucosal disorder [primarily erythema], and nasal septum ulceration) or associated with the underlying disease (acute sinusitis or nasopharyngitis). Most local AEs were identified as a result of intensive active monitoring of all subjects at scheduled intervals by skilled endoscopic nasal examination at each visit and were not spontaneously reported. The majority of these AEs were mild and importantly, are known to have resolved with continued use of study drug. No deaths were reported, 18 subjects receiving OPN-375 reported serious adverse events (SAEs) during the placebo controlled and open-label studies. One placebo-treated subject reported treatment-related SAEs, and the overall rate of discontinuations due to AEs was approximately 4% among all subjects who received OPN-375.

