4 SELECTION AND WITHDRAWAL OF SUBJECTS

4.1 Inclusion Criteria

Potential subjects must meet the following criteria to enter this study:

1. men or women aged 18 years and older at baseline visit
2. women of child-bearing potential must be abstinent, or if sexually active:
 - a. be practicing an effective method of birth control (eg, prescription oral contraceptives, contraceptive injections, contraceptive patch, intrauterine device, double-barrier method [eg, condoms, diaphragm, or cervical cap with spermicidal foam, cream, or gel], or male partner sterilization) before entry and throughout the study, or
 - b. be surgically sterile (have had a hysterectomy or bilateral oophorectomy, tubal ligation, or otherwise be incapable of pregnancy), or
 - c. be postmenopausal (amenorrhea for at least 1 year)
3. women of child-bearing potential must have a negative urine pregnancy test at Visit 1 (Screening)
4. must have a history of CRS and be currently experiencing 2 or more of the following symptoms, one of which has to be either nasal congestion or nasal discharge (anterior and/or posterior nasal discharge) for equal to or greater than 12 weeks:
 - nasal congestion
 - nasal discharge (anterior and/or posterior nasal discharge)
 - facial pain or pressure
 - reduction or loss of smell
5. endoscopic evidence of nasal mucosal disease, with edema, purulent discharge; or polypoid tissue/polyps (<Grade 1) in middle meatus, bilaterally, or presence of bilateral disease on a prior CT scan performed within 14 days of Visit 1
6. must have confirmatory evidence via CT of bilateral sinus disease (have at least 1 sinus on each side of nose with a Lund-Mackay score of ≥ 1)
7. baseline CT scan must show a combined $\geq 25\%$ opacification of the ethmoid sinuses and $\geq 25\%$ opacification of at least 1 maxillary sinus
8. must have at least moderate symptoms (as defined in [Section 7.2](#)) of nasal congestion as reported by the subject, on average, for the 7-day period preceding Visit 1 (Screening) run-in
9. must have an average morning score of at least 1.5 for congestion on the Nasal Symptom Scale (as defined in [Section 7.2](#)) recorded on the subject diary over a 7-day period during the first 14 days of the single-blind -run-in period
10. must demonstrate an ability to correctly complete the daily diary during the run-in period to be eligible for randomization

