6.3 Visits 3, 4, and 5 (Weeks 4, 8, and 12)

During the 24-week double-blind treatment phase, subjects will return to the study site at Weeks 4, 8 and 12 to have efficacy and safety assessments performed.

At all visits during the double-blind treatment phase, treatment compliance will be monitored as described in [Section 5.7](#). Subjects will be given a double-blind- study drug kit (containing 2 devices) assigned through the IWRS at Visit 3/Week 4 and Visit 4/Week 8. Subjects will receive 3 kits at Visit 5/Week 12. Subjects will be instructed to bring the study drug kits with them to each visit.

Subjects will be required to keep a daily diary of nasal symptoms through Week 12. The diary will be completed immediately before the morning and evening doses and will include recording of both instantaneous and reflective scores for nasal symptoms (see [Section 7.2](#)). Subjects will also be instructed that the use of rescue medication for CRS symptoms is not allowed until after the Week 4 visit; starting at the Week 4 visit, they will be instructed to record use of the approved rescue medication in the electronic diary. Subjects will be instructed to bring the diary with them to all study visits.

The site staff will continue to monitor electronic diary transmission reports throughout the first 12 weeks of double-blind treatment to ensure that subjects are recording both morning and evening

nasal symptoms and rescue medication use and that the data are being transmitted to the data base. Site staff should follow-up with subjects as necessary to counsel them on completion of the electronic diaries.

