9.9.1 Adverse Events (AEs)

All reported AEs will be coded using the Medical Dictionary for Regulatory Activities (MedDRA) version 20 or higher. Treatment emergent AEs (TEAEs) are defined as AEs with onset dates on or after the start of double-blind study drug. The incidence of TEAEs during the study period will be tabulated by treatment group and body system (or System Organ Class [SOC] and preferred term) overall, by severity, and by relationship to study drug using subject counts and percent. Those AEs with missing onset dates or missing severity will be included as treatment-emergent. If an AE is reported more than once during the double-blind study phase, the greatest severity and the worst-case attribution will be used for presentation in tables.

Deaths, SAEs, and AEs causing discontinuation of study participation and/or study treatment will be tabulated by treatment group with subject counts and percent. Adverse events for individual subjects will be listed, along with information regarding onset, duration, severity, and relationship to study drug.

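### Section 8.1 bars all non-serious worsening of CRS symptoms from AE reporting, so treatment-related congestion gets no AE entry or causality assessment

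*Protocol*

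**What the plan says.** Protocol Section 8.1 opens with a broad AE definition: "This includes any occurrence that was new in onset or aggravated in severity or frequency from the baseline condition". It then notes that CRS symptoms are collected for the primary and secondary endpoints and instructs that "Changes or worsening of symptoms of CRS should not be reported as AEs". One exception follows: "All events that meet the definition of a SAE will be reported as SAEs, regardless of whether they are protocol-specific assessments".

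What counts as a CRS symptom can be read from Section 4.1. Subjects "must have a history of CRS and be currently experiencing 2 or more of the following symptoms", and the list is congestion, discharge, facial pain or pressure, and reduced or lost smell.

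Section 1.2 describes earlier experience with the product. The commonest AEs on active treatment are grouped as "local effects at the site of administration in the nasal cavity (epistaxis, nasal congestion", followed by mucosal disorder and septal ulceration. Events tied to the underlying disease (acute sinusitis, nasopharyngitis) are named separately.

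On symptom collection, Section 6.3 says: "Subjects will be required to keep a daily diary of nasal symptoms through Week 12". On reporting, Section 9.9.1 says that "AEs causing discontinuation of study participation and/or study treatment will be tabulated by treatment group". It plans no matching table for discontinuations due to CRS worsening.

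**The concern.** Congestion belongs to two categories. It is a symptom of the disease under study, and the sponsor's own summary treats it as a local effect of giving the product. Section 8.1 handles it only as the first. An investigator who believes that the spray or device provoked congestion, and who follows the text, makes no AE entry unless the event is serious.

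The relatedness judgement is lost with the entry, because Section 8.1 asks for it only for AEs, and Sections 8.2 and 8.3 define adverse reactions and suspected adverse reactions as kinds of AE. At stake is whether the TEAE tables for a locally acting nasal product show a reaction that is already known to be common with it.

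**Working it through.** The plan states no figure on this point, so there is none to reproduce. The check has two parts.

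**Does any other route bring the event back as an AE?**

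- *SAE exception (8.1).* It covers serious events only.
- *Discontinuation criterion (8.1).* A list later in the section makes some findings AEs if they lead to discontinuation, need treatment, or accompany clinically important symptoms. It applies to abnormal results of diagnostic procedures and of the nasal examination. A reported symptom with no abnormal finding does not enter through it.
- *Nasal examination (7.4.2, Attachment 3).* Clinically significant findings go on the AE form. The key assessments are epistaxis, septal erosion or perforation, ulceration elsewhere, and candidiasis. These are findings, not symptoms. The examination is scheduled only at Visit 1 and Week 24/ET, whereas Section 1.2 says that most local AEs in earlier studies came from endoscopy at every visit.
- *Aggregate review (8.3).* Known consequences of the disease can become suspected reactions if they are more frequent on drug. That comparison needs AE records, and Section 8.1 stops these for non-serious CRS symptoms.
- *SAP.* Section 2 refers safety analysis to the CS-3205 SAP, which is not among the documents. An analysis rule cannot restore an event that was never entered.

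No route covers a non-serious symptom that is attributed to treatment.

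**How far does endpoint collection stand in for AE reporting?**

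Inputs:

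- double-blind period T = 24 weeks (Section 3.1)
- diary D = 12 weeks (Section 6.3)
- SNOT-22 at baseline and Weeks 4, 8, 12 and 24/ET (Schedule of Study Procedures), with recall R = 2 weeks (Section 7.2)

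Results:

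- Diary share: D / T = 12 / 24 = 50% (84 of 168 days).
- Weeks with no CRS symptom-severity scale: T − D − R = 24 − 12 − 2 = 10 weeks (70 days).
- Share of the treatment period: 10 / 24 = 41.7%.
- Share of the time after Week 12: 10 / 12 = 83.3%.

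These are approximate, since visits have a window of ±7 days.

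The following records remain for those 10 weeks:

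- *Exacerbation assessments at Weeks 16, 20 and 24.* They count a worsening only if it lasts at least 3 days, leads the subject to seek care, and brings an escalation of treatment.
- *Concomitant medications at the same times.* They show what was taken, not how severe the symptom was.
- *PGIC at Week 24/ET.* This is one global rating since the start of study drug.
- *Smell Identification Test at Week 24/ET.* It shows smell at that visit only.

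The Week 16 and 20 contacts also ask about AEs, but under Section 8.1 the answer leaves out non-serious CRS symptoms. Before Week 12 the diary records congestion by arm, as an efficacy score without a causality assessment.

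**The case against.** Keeping fluctuation of the study disease out of the AE tables is a reasonable design choice. Section 8.1 gives its reason and protects SAE reporting. Without some such rule, each bad day of congestion could become an AE and the tables would repeat the efficacy data. This stands, and it is why the exclusion should be narrowed rather than removed.

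A reader might also infer several stronger things, which the documents do not support:

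- *That local intolerance in general goes uncounted.* Epistaxis, ulceration, perforation, candidiasis and other clinically significant examination findings remain AEs. AEs are collected at every visit and contact.
- *That nothing is recorded after Week 12.* The gap is in severity scales. Exacerbations, medications, PGIC and the smell test still give partial information.
- *That stops for intolerance are recoded as lack of efficacy.* Section 4.3 offers that reason, but also provides for stopping on safety or tolerability grounds. Nothing directs a recoding.
- *That the comparison favours OPN-375.* Under Section 5.2, placebo uses an identical device and the same formulation without the drug, so device or excipient effects are lost in all arms. The rule also removes disease worsening, which an effective drug would make more frequent on placebo. The net direction is unknown.
- *That the results cannot be compared with earlier studies.* Their AE reporting rules are not given.

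**Conclusion.** The point holds in a limited form. As written, Section 8.1 removes non-serious intolerance that presents as a CRS symptom, chiefly congestion, from AE counts and from causality assessment. Nothing elsewhere in the two documents restores it. Endpoint collection is a partial substitute up to Week 12 and a weak one for about 10 of the 24 weeks.

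The consequence is under-recording of absolute rates in all arms. Its size cannot be stated, because the documents give no congestion AE rate and no placebo comparison for it. The conclusion assumes that investigators follow the sentence literally and that no CRF guideline outside these documents adds an exception. It does not touch the efficacy analyses, and safety analysis is descriptive. Cheap improvement; low priority.

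**What to change.** In Section 8.1, replace the blanket sentence with: *Worsening of CRS symptoms is not recorded as an AE unless the investigator considers it related to study drug, device or procedure, or it leads to discontinuation of study treatment or of the study, or it meets an SAE criterion.*

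In Section 9.9.1, tabulate discontinuations for CRS worsening by arm, next to discontinuations for AEs, for study treatment and for the study separately. Section 4.4 requires the CRF to hold the reason for leaving the study. The sponsor should confirm that the reason for stopping treatment alone is captured too.

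The cost is a wording change in the protocol and CRF guidance, a few more AE entries and one table. The downside is slight overlap between AE and efficacy reporting for those cases. The new wording acts only from the time it is introduced. The table can still be produced from existing data if the reasons were recorded.

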- ^a All visits up to Visit 6 (Week 24) should be scheduled based on the date of the Day 1 visit. If necessary, visits may be performed within the time window shown; however, subsequent visits should be scheduled based on the date of the Day 1 visit.
- ^b The assignment of a kit number for the demonstrator model EDS is not performed by IWRS, rather, the study staff will dispense a demonstrator model EDS kit and record the kit number in the drug dispensing log. This practice EDS is only used at the site at Visit 1 (Screening) and is not to be sent home with the subject.
- ^c Women of child-bearing potential only; urine pregnancy tests will be performed at each visit, not including subject contacts. Subjects continuing treatment past Week 24/Visit 6 will need an additional pregnancy test completed upon returning to site.
- ^d Nasoendoscopy will be performed using a rigid or flexible endoscope. The examiner must be able to visualize the middle meatus with the scope. Decongestants and/or local anesthetics may be used for the nasoendoscopic procedure.
- ^e The CT scan should be performed after diary eligibility is confirmed and prior to Day 21 of the screening run-in period.
- ^f For the Week 24 study visit, the CT examination should be performed prior to the on-site visit.
- ^g Demonstrator model EDS kit (see footnote b) and single-blind placebo dispensation only.
- ^h At Visit 1 (Screening), the IWRS will be contacted to obtain the subject ID number, the identifier for the single-blind kit to be dispensed and to track enrollment. IWRS will be contacted at Visit 2 to randomly assign subjects to treatment. At Visit 2 through – Visit 5, IWRS will be used to assign the study

drug kit(s) to be dispensed. If a subject cannot complete the EOS CT scan at Visit 6 (Week 24), study staff should not complete Visit 6 in IWRS. Subjects should continue study treatment until an EOS CT scan can be completed. Study staff will dispense additional study medication via the “Unscheduled Visit” functionality in IWRS. IWRS will be contacted for each ‘Unscheduled Visit,’ at which time one treatment kit will be dispensed.

- i The period of observation for collection of AEs extends from the time the subject gives informed consent until completion of the double-blind treatment period or an early termination visit. Serious adverse events will be reported through 30 days after the last dose of study drug administration.

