2.5 Number of Subjects and Duration of Study

The total planned number of subjects is approximately 210. Approximately 210 subjects will be randomly assigned to receive 1 of the 2 active treatments or placebo (70 subjects in each group); subjects will be randomized using a 1:1:1 ratio.

The expected participation period for a subject is approximately 26 weeks, including a pretreatment phase consisting of a Screening visit followed by a 7- to up to 21-day single-blind- placebo run-in period and a 24-week double-blind treatment phase.

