4.3 Withdrawal and Removal of Subjects

Subjects will be informed that they are free to withdraw from study treatment and/or the study at any time at their own request without prejudice to their future medical care, or that they may be withdrawn at any time at the discretion of the investigator or Sponsor for safety, nonadherence to protocol requirements, or administrative reasons (eg, termination of study by Sponsor). Subjects wishing to withdraw from study treatment will be strongly encouraged to continue in the study and have all scheduled study procedures performed.

A subject must be withdrawn from treatment for the following reasons:

- subject becomes pregnant
- A subject's study treatment will be discontinued if the investigator or Sponsor considers it in the subject's best interest to stop treatment, (eg, for safety or significant tolerability reasons such as an AE). Subjects who have one of the following AEs must be withdrawn from study treatment.
- IOP of >21 mm Hg
- nasal septal perforation
- new onset or worsening of cataract

A subject may also be withdrawn from study treatment for the following reasons:

- lack of efficacy
- protocol violation

A subject may be withdrawn from the study for the following reasons:

- withdrawal of consent
- adverse event
- protocol violation that makes it unsafe for the subject to continue in the study
- termination of the study
- lost to follow up
- public health measure
- other

If a subject withdraws from the study after starting study treatment, appropriate follow-up must be conducted wherever possible.

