8.5.2 Serious Adverse Event Reporting

All SAEs must be reported within 24 hours to:

PPD

Safety Email: [contact]

Safety [contact]

Note: If the contact information above changes during the course of the study, written notification will be provided by the Sponsor or their designee to the investigator, and a protocol amendment will not be required.

It is imperative that PPD be informed within 24 hours after the investigator becomes aware of a SAE so that reporting to the Regulatory Agencies can be met within the required time frame (7 or 15 calendar days).

Because of the need to report to health authorities all SAEs in a timely manner, it is vitally important that an investigator report any AEs that would be considered serious within 24 hours, even if the investigator does not consider the AE to be clinically significant or drug-related.

Should the investigator become aware of an SAE (regardless of relationship to study drug) that occurs within 30 days after stopping the study drug, the SAE must be reported in accordance with the procedures specified in this protocol. There is no time limit on the collection of SAEs that are considered related to study drug.

All SAEs that are not resolved by the end of the study, or that were not resolved upon discontinuation of the subject's participation in the study, are to be followed until either: the AE resolves, the AE stabilizes, the AE returns to baseline values (if a baseline value is available), or it is shown that the AE is not attributable to the study drug or study conduct.

Medical and scientific judgment is to be exercised in deciding whether expedited reporting is appropriate in other situations, such as for important medical events that were not immediately life-threatening or did not result in death or hospitalization but are jeopardizing the subject or require intervention to prevent one of the outcomes listed above.

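### The treatment-emergent rule uses onset date alone and lets missing severity override it; the AE and SAE collection windows also need to be reconciled

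*Protocol*

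**What the plan says.** **Treatment-emergent status.** Protocol Section 9.9.1 states that TEAEs "are defined as AEs with onset dates on or after the start of double-blind study drug". It gives no end date and does not mention worsening. It adds: "Those AEs with missing onset dates or missing severity will be included as treatment-emergent".

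**What counts as an AE.** Section 8.1 includes an occurrence that has become more severe or more frequent than at baseline. Collection starts at consent, before the 7- to 21-day placebo run-in. The investigator assigns one maximum severity per AE. Section 7.4.2 puts clinically significant nasal findings on the AE form from Visit 1 onward.

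**Collection windows.** Footnote i of the Schedule of Study Procedures collects AEs "until completion of the double-blind treatment period or an early termination visit"; Section 8.1 collects them "until completion of the end-of-study visit or an early termination visit". For serious events, Section 8.1 says "SAEs will be reported through 30 days after the last dose of study drug administration", and Section 8.5.2 requires reporting, whatever the relationship to drug, of an SAE "that occurs within 30 days after stopping the study drug". Section 8.5.2 sets no time limit for related SAEs.

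**Follow-up off drug.** Section 4.3 says: "Subjects wishing to withdraw from study treatment will be strongly encouraged to continue in the study and have all scheduled study procedures performed". Section 6.5 keeps some subjects on drug beyond Week 24 until the final CT can be done.

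**SAP.** Section 2 declares no deviations from the protocol amendment and makes the CS-3205 SAP the main reference for safety endpoints, definitions and data handling. The CS-3206 SAP has no TEAE rule of its own.

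**The concern.** TEAE status decides which events enter the main safety tables by arm. Two of the stated rules can put an event on the wrong side of that line.

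The first can leave out an event that worsened on drug. It bears on the expected local effects: Protocol Section 1.2 lists epistaxis and nasal septum ulceration among the commonest AEs in the active groups. Exclusion criterion 12 bars only subjects with more than one frank epistaxis episode in the month before Visit 1, so some subjects can enter with a history of bleeding.

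The second can bring in an event that began before double-blind drug, for a reason unrelated to timing.

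A third feature is that the definition has no end, while the protocol deliberately keeps subjects in the study after they stop drug. Events that start long after the last dose are then mixed with on-drug events. For the same subjects, the windows for AEs and SAEs are tied to different anchors, the last visit and the last dose, and the text does not say how the two fit together.

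**Working it through.** The plan gives no figure on this point, so there is none to reproduce. The first check applies the rules to each kind of record; the second is date arithmetic.

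**1. Section 9.9.1 applied to each case**

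| Event | Status as written | Comment |
|---|---|---|
| Run-in onset, no change, severity recorded | Not a TEAE | Correct |
| Run-in onset, worsens on double-blind drug, same record | Not a TEAE | Onset date is unchanged; only the maximum severity moves. Section 8.1 treats the worsening as an AE |
| Run-in onset, worsens, site opens a new record | TEAE | Correct, but no text requires the new record |
| Run-in onset known, severity missing | TEAE | Contradicts the onset definition |
| Onset date missing | TEAE | Reasonable cautious default |
| Onset in off-drug follow-up | TEAE | No end date; bounded only by the end of AE collection |

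Rows 2 and 4 are the errors. Rows 2 and 3 also show that the same clinical course can be classified either way, depending on how the site completes the form.

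**2. Distance between last dose and last visit**

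Inputs: "a 24-week double-blind treatment phase" (Section 2.5), so the last visit is at 24 × 7 = Day 168, with a window of ±7 days (Schedule); and 30 days after the last dose (Sections 8.1 and 8.5.2).

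- Off-drug follow-up = 168 − day of last dose.
- Time from the 30-day mark to the last visit = 168 − (day of last dose + 30).

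| Last dose | Off-drug days to Day 168 | 30-day mark | Days from mark to Day 168 |
|---|---|---|---|
| First dose only (Day 0) | 168 | Day 30 | 138 |
| Week 4 (Day 28) | 140 | Day 58 | 110 |
| Week 8 (Day 56) | 112 | Day 86 | 82 |
| Week 12 (Day 84) | 84 | Day 114 | 54 |
| Week 16 (Day 112) | 56 | Day 142 | 26 |

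The 30-day mark precedes the last visit for any last dose before Day 168 − 30 = 138. The visit window moves each entry in the last column by 7 days either way. For a subject dosed to Day 168, the mark falls 30 days after the last visit, so there the sentence extends collection.

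**3. Share of follow-up time, by assumption**

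The documents give no rate of stopping drug and staying in the study. Suppose 10% of an arm stop at Week 8 on average and stay to Day 168.

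- Off-drug share of the arm's follow-up: 0.10 × 112/168 = 6.7% (3.3% at a 5% stopping rate, 13.3% at 20%).
- Share beyond the 30-day mark: 0.10 × 82/168 = 4.9% (2.4% to 9.8%).

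These are shares of person-time, not of events.

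**4. The SAE passages side by side**

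Sections 8.1 and 8.5.2 give the 30-day limit. Section 8.1 also collects AEs to the last visit, requires each to be classed as serious or not, and says that events meeting the SAE definition are reported as SAEs. Section 8.5 requires SAEs to be reported within 24 hours and gives no end date. Section 8.5.2 leaves related SAEs open-ended. The 30-day sentence can therefore be read as a cut-off for unrelated SAEs or as an extension past the last visit.

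**The case against.** **The CS-3205 SAP may settle it.** Protocol Section 9 leaves detailed definitions to the SAP, and that SAP could hold a worsening rule, an end date or a missing-data rule. This stands as a limit on what can be concluded: the rules in Section 9.9.1 cannot be assumed to be the final operative ones. It does not excuse the protocol text, because the CS-3206 SAP declares no deviations and any different rule should be stated openly.

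**Sites may open a new record when an event worsens.** Section 8.1 asks for changes in AEs to be documented, and Section 9.9.1 foresees an AE being reported more than once in the double-blind phase. A miss is therefore not certain in every case. But nothing requires a new record or says that the date of worsening counts as onset.

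**Missing severity should be rare.** The investigator must grade severity, and Section 10.1 treats forms as complete only once missing data are resolved. This limits the effect, but the rule is still wrong when it applies.

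**An open-ended definition is an inclusive choice.** This is fair. A 30-day end is a convention, and its absence is not an error. Safety analysis is descriptive and onset is listed by subject, so off-drug events can be identified. That supports separate display, not a compulsory cut-off.

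**No collection gap is shown after Week 24.** Section 6.5 provides safety contacts about every 4 weeks until a delayed CT. The difference between footnote i and Section 8.1 is therefore one of wording to reconcile.

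**Conclusion.** Two rules in Section 9.9.1 give wrong results if followed as written: status by onset date alone, and missing severity as a ground for treatment-emergent status. Both conclusions follow from the text, subject to the unseen CS-3205 SAP. How many events are affected cannot be estimated from the documents.

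The missing end date is a matter of presentation. Its extent ranges from 56 off-drug days after a Week 16 stop to 168 after a single dose, if the subject stays to Day 168.

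A reader might infer two stronger things that the documents do not support:

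- **That serious events are lost for months after early stopping.** The 110 days after a Week 4 stop (110/168 = 65% of the double-blind phase) is correct arithmetic, but AEs are collected and classed for seriousness to the last visit, SAEs are to be reported, and related SAEs have no limit. What remains is doubt over whether unrelated SAEs in that interval are reportable.
- **That comparison of safety between arms becomes unreliable.** No count of misclassified events supports this, and the subject listings show onset dates.

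**What to change.** 1. **Section 9.9.1, definition.** Define a TEAE as an AE with onset, or worsening in severity or frequency, on or after the first double-blind dose. State how the date of worsening is recorded, for example by a new AE record.
2. **Section 9.9.1, missing data.** Apply the default to missing onset dates only. Deal with missing severity only in the by-severity table.
3. **Off-drug events.** Flag or tabulate separately the events that start in follow-up after the last dose.
4. **CS-3205 SAP.** Confirm that its TEAE and missing-data rules agree, and state any difference in the CS-3206 SAP.
5. **Secondary.** Reconcile Sections 8.1, 8.5 and 8.5.2 and footnote i, so that they give one end to AE collection, including when the final CT is delayed, and one statement on whether unrelated SAEs in off-drug follow-up are reportable.

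The cost is wording in these sections, a line of instruction to sites on recording worsening, and one extra table. If item 5 settles on the wider reading, a few more SAE reports may come from subjects off drug. The efficacy analysis and the sample size are unaffected.
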